### **2. STUDY PLAN**

#### **2.1 Study Design**

This is a randomized, open-label phase II study designed to evaluate the safety and efficacy of etoposide in patients with COVID-19 infection. Treatment will be comprised of etoposide administered intravenously at a dose of 150 mg/m^2 on Days 1 and 4 in patients with COVID-19 infection meeting eligibility criteria. Subsequent doses of etoposide will be allowed if the investigator and treating physician believe the patient had clinical benefit from etoposide therapy but subsequently has evidence of recurrent clinical deterioration.

Two cohorts of patients will be treated with etoposide. Cohort 1 will be patients who require intubation due to their severe COVID-19 related respiratory illness. Cohort 2 will be COVID-19 patients who have progressive pulmonary dysfunction and evidence of severe inflammation but who are not yet intubated. Although prior treatment for COVID with anti-cytokine therapy will not exclude a patient from enrollment on this trial, a “washout” period of at least 3 half-lives will be required prior to initiation of etoposide therapy. Enrollment will begin with cohort 1, following which a decision will be made to open cohort 2 or not, as outlined further in this document.

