## **4. INVESTIGATIONAL PLAN**

### **4.1 Overall Design**

Open-label, randomized Phase II study of etoposide administered intravenously at a dose of 150 mg/m^2 once daily on Days 1 and 4 for a total of two doses to inpatient patients with moderate and severe COVID-19 who have consented to treatment on this clinical trial. Dose reductions will be performed as outlined in Section 5.

This study includes a screening period, a treatment period, and a follow-up period for adverse events that will include the remainder of hospitalization, with additional assessments at days 30 and 60 as outlined in the study calendar (Section 6). After obtaining informed consent, the patients randomized to etoposide will begin treatment with the study drug. Subjects randomized to control will receive standard of care treatment. No placebo will be used. Subjects will be monitored for adverse events and to evaluate study outcomes. Patients removed from the study due to any unacceptable adverse events will also be followed until time of death or hospital discharge.

For patients randomized to standard of care, day 1 will be considered day of randomization. These patients will be followed to record the outcome of all primary and secondary objectives until time of death or hospital discharge, whichever occurs earlier.

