## 6. STUDY PROCEDURES & CALENDAR

REQUIRED STUDIES	Screening	Day 1, Day 4 and Day 7 Σ#	Prior to discharge	Day 30*
PHYSICAL				
History & Physical Exam	X	X	X	X
Height, Weight, Body Mass Index, and Body Surface Area	X			
Vital Signs	X	X	X	X
Toxicity Notation	X	X	X	X
Respiratory Status on 8 point scale ^	X	X	X	X
HISTORY				
Concomitant medicines (including COVID therapies, ie hydroxychloroquine, tocilizumab, anakinra) with date of initiation	X			
Smoking status	X			
Comorbidities	X			
Symptoms, including date of symptom onset	X			
LABORATORY				
Beta HCG (for women of childbearing potential)	X			
CBC with Differential +	X	X	X	X
Comprehensive metabolic panel +	X	X	X	X
Lactate Dehydrogenase	X	X	X	X
D-dimer	X	X	X	X
Ferritin	X	X	X	X
C-reactive protein	X	X	X	X
PaO 2 /FIO 2 (P/F) ratio (cohort 2 only)	X	X	X	X
INR (if on warfarin) Ω	X			
ADDITIONAL TESTING				
Electrocardiogram (ECG)	X			

# For subjects randomized to treatment, the data for Day 1 and Day 4 will be collected prior to the etoposide dose (within 24 hours).

\*Information to be obtained as feasible, if patient has been discharged attempts will be made to obtain the information from the patient's primary care provider. If such results are not available, participant will be contacted by the research nurse to assess toxicities.

^ Mortality assessment (included on the 8 point scale) will also be recorded at Day 14 and 60, in addition to Day 30 mentioned above

+ CBC and comprehensive metabolic panel will be measured at least twice weekly during hospitalization. These tests will also be obtained pre-dose 8, 11, 18, and 25 for those patients who require additional etoposide dosing as described above (Section 4.3 and 5.3)

Ω INR to be repeated at least twice weekly for patients on warfarin

Σ Day 1 of treatment for patients randomized to standard of care (SOC) will be considered the day of randomization

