## 7.2 Statistical Analysis

Tabulations overall, and by treatment group, will be produced for appropriate demographic, baseline, efficacy, and safety parameters, with number and percentages reported for categorical variables and the mean, median, standard deviation, and range for continuous variables. All analyses will be performed at an  $\alpha=0.05$  level using SAS v.4.

Efficacy analyses will be performed in an intention-to-treat (ITT) population consisting of all patients randomized. The difference in ordinal scale improvement rates between treatment arms will be calculated with a 95% confidence interval and formally compared using Fisher's Exact Test. For secondary analysis of the primary endpoint, logistic models individually adjusted for age, diabetes, chronic lung disease/moderate or severe asthma, immunocompromise, liver disease, heart disease/hypertension, smoking and obesity (BMI  $> 40$ ), residence in long-term care facility, will also be examined with odds ratios and 95% confidence intervals reported.

The analysis of secondary time to event endpoints including survival at 30 days, duration of hospitalization, duration of ventilation and ventilator free days, will be compared between treatment arms based on a log-rank test. The median will be estimated with a 95% CI for each treatment arm using the Kaplan-Meier method. Cox proportional Hazards models adjusted individually for age, diabetes, chronic lung disease/moderate or severe asthma, immunocompromise, liver disease, heart disease/hypertension, smoking and obesity (BMI  $> 40$ ), residence in long-term care facility, will also be examined with odds ratios and 95% confidence intervals reported. Changes in inflammatory markers and in oxygenation or  $\text{paO}_2/\text{FIO}_2$  ratio, based on available recorded measurements, will be compared between treatment arms using a two sample t-test, or a Wilcoxon Rank Sum test, as appropriate. Incidence of grade 3 or 4 AEs and serious AEs will be compared using Fisher's Exact test.

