## 8. MEASUREMENT OF EFFECT

### 8.1 Definitions

**Evaluable for toxicity:** All participants who receive at least one dose of study treatment will be evaluable for toxicity from the time of their first treatment.

**Evaluable for objective response:** Only those participants who have received at least one dose of etoposide will be eligible for objective response.

For purposes of data collection, day 1 of patients on the standard of care arm will be the day of randomization.

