### **10. DATA MANAGEMENT**

#### **10.1 Analyses and Reporting**

Data generated by the methods described in the protocol will be recorded in the subjects' medical records and/or study progress notes. The investigator will be the assessor of the primary endpoint. Data will be directly inputted into an electronic system. Data will be analyzed and reported after study is completed or meaningful endpoints are reached. All subsequent data collected will be analyzed and reported in a follow-up clinical report.

The index data for patients on treatment is the day 1 dose of etoposide. For patients enrolled into the standard of care arm, day 1 will be the day of randomization.

The Principal Investigator at BMC/BU Medical Campus will report Unanticipated Problems, safety monitors' reports, and Adverse Events to the BMC/BU Medical Center IRB and FDA in accordance with established policies:

- Unanticipated Problems occurring at BMC/BU Medical Campus will be reported to the IRB within 7 days of the investigator learning of the event.
- Unanticipated Problems occurring at BMC/BU Medical Campus will be reported to the FDA within 15 days of the investigator learning of the event.
- Unexpected fatal or life-threatening suspected adverse events occurring at BMC/BU Medical Campus will be reported to the IRB within 7 days of the investigator learning of the event.
- Reports from the designated medical monitor with recommended changes will be reported to the IRB within 7 days of the investigator receiving the report.
- Adverse Events (including Serious Adverse Events) will be reported in summary at the time of continuing review, along with a statement that the pattern of adverse events, in total, does not suggest that the research places subjects or others at a greater risk of harm than was previously known.

- Reports from designated medical monitor with no recommended changes will be reported to the IRB at the time of continuing review.

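### Day 1 is the first dose in the etoposide arm but randomization in the control arm, and the response-evaluable definition contradicts the intention-to-treat rule

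*Combined protocol and SAP*

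**What the plan says.** Section 10.1 sets the index day by arm. For the etoposide arm, "The index data for patients on treatment is the day 1 dose of etoposide". For controls, "For patients enrolled into the standard of care arm, day 1 will be the day of randomization". The control half recurs in section 4.1 ("For patients randomized to standard of care, day 1 will be considered day of randomization"), in a footnote to the section 6 calendar and in section 8.1 ("day 1 of patients on the standard of care arm will be the day of randomization"), so it is a settled rule and not a slip.

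The same calendar says that, for patients randomized to treatment, "the data for Day 1 and Day 4 will be collected prior to the etoposide dose (within 24 hours"). The etoposide arm's Day 1 score on the 8-point scale is thus tied to the dose and not to randomization. Screening also includes an 8-point score. No section says which of the two is the baseline for the two-category improvement.

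On the analysis population, section 7.2 states: "Efficacy analyses will be performed in an intention-to-treat (ITT) population consisting of all patients randomized". Section 8.1 states: "Only those participants who have received at least one dose of etoposide will be eligible for objective response".

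The primary outcome is assessed at Day 14 (7.1), and the key secondary endpoint is survival at 30 days (2.5). Neither section, nor 7.2 or 8.2, gives a time origin, so the index in 10.1 is the only one a programmer could use for them.

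**The concern.** A randomized comparison needs the same time zero in both arms, no later than randomization. Here, an etoposide patient dosed k days after randomization reaches Day 14 at 14 + k days after randomization, and a control reaches it at 14. In acute respiratory failure a few days can change a patient's category. The trial is open-label, and the investigator assesses the primary endpoint (10.1).

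A second gap is one-sided. A patient randomized to etoposide who dies, withdraws or passes a laboratory limit before dosing has no Day 1, hence no defined Day 14 or Day 30. No control can fall into that gap. The plan needs a rule for such patients, and the two sentences that might supply one, in 7.2 and 8.1, disagree. The disagreement remains even if every patient is dosed on the day of randomization.

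At stake are the estimates for the primary and key secondary endpoints, and which patients they describe.

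**Working it through.** **Inputs from the documents.** Control response 30% and etoposide response 80% at Day 14, with 24 etoposide and 8 control patients per cohort (7.1); Fisher's exact test (7.2). **Assumed, because the documents give no value:** a delay k of 1 to 3 days from randomization to first dose, 30-day mortality of 30 to 50%, and the shape of the hazards.

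**The plan's own figure.** The stated 80% power is roughly reproduced by the unpooled normal approximation: Φ(0.5/√(0.3×0.7/8 + 0.8×0.2/24) − 1.96) = 78.7%. Nothing below depends on it, and a common time zero leaves the sample size unchanged.

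**1. Response, baseline fixed at or before randomization.** With a constant recovery hazard, an inert drug shows 1 − 0.7^((14+k)/14) at its own Day 14:

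| Delay k (days) | Control | Etoposide arm, inert drug | Difference |
|---|---|---|---|
| 0 | 30.0% | 30.0% | 0 |
| 1 | 30.0% | 31.8% | +1.8 points |
| 2 | 30.0% | 33.5% | +3.5 points |
| 3 | 30.0% | 35.2% | +5.2 points |

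Counting Day 1 to Day 14 as 13 days gives 31.9%, 33.7% and 35.5%. On that count, the chance that the two-sided Fisher test rejects with no drug effect is 2.8% without delay and 2.7 to 3.1% with a delay of 1 to 3 days.

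**2. Response, baseline at the pre-dose Day 1 score.** Both arms then have the same length of follow-up from baseline. Under a constant hazard, patients not yet recovered at dosing show 30% at their own Day 14, so the gain in step 1 disappears. What remains is a baseline measured after randomization in one arm. A patient who moved from category 6 to 5 before dosing must reach 3 instead of 4 to respond. One who moved from 6 to 7 need reach only 5. The net direction cannot be determined.

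**3. Undosed patients.** If the etoposide rate is p of 24 and one undosed non-responder is dropped, it becomes 24p/23, a rise of p/23: 0.30/23 = 1.3 points, or 0.80/23 = 3.5 points. For several patients, take 80% response among the dosed, rounded to whole patients. Two undosed gives 18/22 = 82% if dropped and 18/24 = 75% if kept as non-responders. Four undosed gives 16/20 = 80% against 16/24 = 67%.

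**4. Survival, no drug effect.**
- All deaths kept, etoposide window 30 + k days, constant hazard: 1 − (1 − m)^((30+k)/30). True mortality m of 30% reads 30.8 to 32.5%, and 50% reads 51.1 to 53.3%. The error is against etoposide.
- Deaths before dosing dropped, constant hazard: mortality from dose is unchanged.
- Deaths before dosing dropped, early-weighted hazard (Weibull, shape 0.7): 30% reads 28.2 to 26.7%, and 50% reads 47.5 to 45.3%. The error favours etoposide by about 2 to 5 points.

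The sign therefore depends on how 7.2 and 8.1 are reconciled and on when deaths occur.

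**The case against.** The strongest reply is that the delay may be close to nil. Patients are already inpatients at one site, the drug is commercially available, and 4.1 has patients randomized to etoposide begin treatment. With same-day dosing the clock effect is exactly zero. This stands as a limit on size. It does not close the gap, because no section requires same-day dosing or sets a maximum interval.

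Several stronger readings are tempting, and the documents do not support them:

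- *The washout causes delay.* Section 2.1 says a "period of at least 3 half-lives will be required prior to initiation of etoposide therapy", which might suggest waiting after randomization. But 3.3 makes anti-cytokine treatment within three half-lives an exclusion, so an eligible patient has already completed it.
- *The dosing limits in 5.5 will often block the first dose.* Its bilirubin and creatinine clearance omission limits equal the 3.3 exclusions, and its neutrophil limit (500) is below the entry limit (1000). They affect a first dose only if values worsen after screening.
- *The plan is biased towards etoposide.* That needs a delay and a baseline fixed at randomization. Neither is stated, and steps 2 and 4 show that the sign can change.
- *Deaths before dosing cannot count.* Under 7.2 every randomized patient is analysed, and death is category 8 of the scale. Immortal time arises only if 8.1 or the dose-based index overrides 7.2.
- *Hospital and ventilator durations shift by the delay.* No section gives their start point. Cohort 1 patients are already intubated at entry, so admission or intubation is an equally available origin.
- *The intention-to-treat analysis is abandoned.* Section 7.2 expressly governs efficacy. Section 8.1 contradicts it but does not clearly replace it.

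It is also fair that the effect on the Fisher test is minor, and that 7.1 claims only initial evidence of efficacy.

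**Conclusion.** The point holds as an inconsistency in time zero and in the analysis population. Section 10.1 gives the arms different origins, the randomization-to-dose interval is uncapped, undosed etoposide patients have no Day 1, and 8.1 conflicts with 7.2. These follow from the text without any assumption.

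Neither the size nor the direction of bias is established. Under the stated assumptions (baseline at randomization, constant hazard, 1 to 3 days' delay), an inert drug would show about 32 to 35% against 30%. With the pre-dose score as baseline the direction is uncertain, and with same-day dosing the clock effect is nil. Each undosed non-responder dropped adds 1.3 points at a 30% rate and 3.5 points at 80%. The harm is to the estimates more than to the type I error. It should be fixed, because the wording defines the primary and key secondary endpoints.

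**What to change.** In 4.1, 6, 8.1 and 10.1:

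- Define time zero as the day of randomization in both arms for Day 14 response and for 30- and 60-day survival. Use the same origin for any duration measured from study entry, and state the origin of the others.
- Name the last 8-point score at or before randomization as the baseline.
- Keep dose day only for drug administration and exposure-related safety, and report the randomization-to-dose interval.
- Replace the 8.1 sentence on response with all randomized participants, regardless of dosing, to agree with 7.2.

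The cost is wording only. The screening score is already in the calendar, randomization already anchors the control arm, and the sample size does not change. The one downside is that etoposide patients dosed late will have had slightly less time on drug at Day 14.

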## **10.2 Data Safety Monitoring**

Toxicity and accrual monitoring will be performed on a routine basis by the study investigators. Subjects will undergo toxicity assessment and laboratory tests according to the study calendar in Section 7. The clinical status and laboratory reports of the study participants will be assessed routinely by the co-investigators throughout the study. The investigators, Medical Monitor and data analyst will remain as broadly informed as possible regarding emerging evidence from related studies as well as from the conduct of this protocol.

In addition, a Medical Monitor has been appointed to provide additional data safety monitoring. The Medical Monitor is a qualified clinician with relevant expertise, but no direct connection with the research, whose primary responsibility is to provide independent safety monitoring in a timely fashion. The PI will submit a report to the Medical Monitor which will include a list of all adverse events and serious adverse events (regardless of relatedness). In addition, any unanticipated problems involving risks to participants or others and participant deaths will be reported to the monitor as soon as possible and within 24 hours. Additional data may be requested by the Medical Monitor, and interim statistical reports may be generated as deemed necessary and appropriate.

The Medical Monitor is expected to provide a formal, unbiased written report evaluating individual and cumulative participant safety data. Although the PI is responsible for assigning causality and expectedness, the medical monitor will comment on whether or not he is in agreement. As an outcome of each review, the Medical Monitor will make a recommendation as to the advisability of proceeding with study intervention, and to continue, modify, or terminate this trial.

Medical Monitor reports will be submitted to the PI following each review which the PI will, in turn, submit to the IRB. The study will not stop enrollment awaiting these reviews, though the Medical Monitor may recommend temporary or permanent cessation of enrollment based on their safety reviews.

Additional monitoring will also be performed by the COVID Research Committee after 10 patients have been randomized in cohort 1. At that time, the committee will determine whether they feel that enrollment may be expanded to include cohort 2, or may request that data be presented again when all patients on cohort 1 have been treated.

## **10.3 Study Monitoring and Auditing**

Investigator responsibilities are set out in the ICH guideline for Good Clinical Practice (GCP) and in the US Code of Federal Regulations (CFR).

Investigators must enter study data onto CRFs or other data collection system. The Investigator will permit study-related monitoring visits and audits by IRB/EC review, and regulatory

inspection(s) (e.g., FDA, EMEA, TPP), providing direct access to the facilities where the study took place, to source documents, to CRFs, and to all other study documents.

## **11. REGULATORY CONSIDERATIONS**

### **11.1 Protocol Amendments**

Any amendment to this protocol must be agreed to by the Principal Investigator. Written verification of IRB approval will be obtained before any amendment is implemented.

### **11.2 Protocol Deviations**

When an emergency occurs that requires a deviation from the protocol for a subject, a deviation will be made only for that subject. A decision will be made as soon as possible to determine whether or not the subject (for whom the deviation from protocol was effected) is to continue in the study. The subject's medical records will completely describe the deviation from the protocol and state the reasons for such deviation. In addition, the Investigator will notify the IRB in writing of such deviation from protocol. Non-emergency minor deviations from the protocol will be permitted with approval of the Principal Investigator.

### **11.3 Institutional Review Board/Ethics Committee Approval**

The protocol for this study has been designed in accordance with the general ethical principles outlined in the Declaration of Helsinki. The review of this protocol by the IRB/EC and the performance of all aspects of the study, including the methods used for obtaining informed consent, must also be in accordance with principles enunciated in the declaration, as well as ICH Good Clinical Practice Guidelines, Title 21 of the Code of Federal Regulations (CFR), Part 50 Protection of Human Subjects and Part 56 Institutional Review Boards.

The Investigator will be responsible for preparing documents for submission to the relevant IRB/EC and obtaining written approval for this study. The approval will be obtained prior to the initiation of the study.

The approval for both the protocol and informed consent must specify the date of approval, protocol number and version, or amendment number.

Any amendments to the protocol after receipt of IRB/EC approval must be submitted by the Investigator to the IRB/EC for approval. The Investigator is also responsible for notifying the IRB/EC of any serious deviations from the protocol, or anything else that may involve added risk to subjects.

Any advertisements used to recruit subjects for the study must be reviewed and approved by the IRB/EC prior to use.

## 11.4 Study Records Requirements

The Investigator must ensure that the records and documents pertaining to the conduct of the study and the distribution of the study drug, that is copies of CRFs and source documents (original documents, data, and records [e.g., hospital records; clinical and office charts; laboratory notes; memoranda; subject's diaries or evaluation checklists; SAE reports, pharmacy dispensing records; recorded data from automated instruments; copies or transcriptions certified after verification as being accurate copies; microfiches; photographic negatives, microfilm, or magnetic media; x-rays; subject files; and records kept at the pharmacy, at the laboratories, and at medico-technical departments involved in the clinical study; documents regarding subject treatment and study drug accountability; original signed informed consents, etc.]) be retained by the Investigator for as long as needed to comply with institutional policies, which generally requires records to be kept for 7 years after closure of the clinical trial. The Investigator agrees to adhere to the document/records retention procedures by signing the protocol.

